9.3. Withdrawal Criteria

Subjects will be advised that they are free to withdraw from the study at any time. Reasons that subjects may discontinue or be withdrawn from the study may include, but are not limited to:

- AEs
- Subject request
- Investigator decision
- Protocol non-compliance
- Study termination by the Sponsor or Institutional Review Board (IRB).

If a subject is withdrawn from the study, all efforts will be made to complete the Visit 3 (EOT) procedures at an Early Termination visit (see [Section 11.2.4](#)). All information, including the reason for withdrawal, should be reported on the applicable pages of the electronic case report form (eCRF).

For subjects who are lost to follow-up, three documented attempts will be made to contact the subject for follow-up information, including reason for discontinuation and follow-up of AEs. Subjects who withdraw from the study will not be replaced.

10. STUDY DESIGN

10.1. Summary of Study Design

This is a double-blind, randomized, placebo-controlled, parallel group study of the efficacy and safety of multiple doses of tolperisone administered TID in approximately 400 male and female subjects experiencing back pain due to or associated with muscle spasm. The tolperisone groups consist of dose levels of 150, 300, 450, and 600 mg administered TID in doses of 50, 100, 150, or 200 mg for 14 days, with a visit at 28 days as follow-up. Subjects randomized to the placebo group will receive matching placebo tablets TID for 14 days. Subject participation will be approximately 4 weeks.

Subjects will be screened for eligibility for participation in the study at Screening/Baseline Visit 1 (Day 1) after reviewing and signing the informed consent form. Subjects meeting all inclusion/exclusion criteria will then be randomized into the study (Day 1) and begin dosing this same day. If needed, screening assessments may be completed up to 3 days prior to Day 1 (first dose) as described below.

It is highly recommended to complete all screening and baseline assessments on the same day the subject presents at the site due to their acute pain relief needs. However, to accommodate real world logistical issues and time constraints of either the subject or site, the site has the flexibility to allow completion of screening assessments within 3 days (-3 days) prior to Day 1 baseline assessments, deployment of study-provisioned smartphone/download of trial application on subject's smartphone, randomization, and first dose (in that order).

After completing all screening and baseline assessments by/on Day 1, subjects will receive all study drug and rescue medication (acetaminophen 500 mg) and will be instructed to begin taking their study drug that same day. Depending on the time of their clinic visit, they should be instructed to begin dosing with either the midday dose (12-2 pm) or the evening dose (6-8 pm). Subjects will be instructed to continue taking study drug TID through Day 14 and complete dosing diary and daily ePRO assessments.

Subjects will return to the clinic to complete the procedures listed in the Schedule of Procedures on Day 4 (± 1 day; Visit 2) and Day 14 (+1 day, End of Treatment [EOT] visit, Visit 3). Subjects must also return to the clinic for a follow-up visit on Day 28 (+3 days, 2-week follow-up visit, Visit 4).

For all subjects, safety laboratory assessments will be performed on Day 1 (Screening/Baseline visit, -3 to 0 days) and Day 14 (Visit 3). In addition, a sample for genotyping will be collected on Day 1 (Screening/Baseline visit). For select sites with additional consenting subjects, pharmacokinetic samples will be collected on Day 4 (Visit 2).

Please refer to Schedule of Procedures, [Table 2](#).

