Study Design: 
This is a double-blind, randomized, placebo-controlled, parallel group study of the efficacy and safety of tolperisone or placebo administered as multiple doses three times a day (TID) in approximately 400 male and female subjects experiencing back pain due to or associated with muscle spasm. The tolperisone groups consist of dose levels of 150, 300, 450, and 600 mg administered TID in doses of 50, 100, 150, or 200 mg for 14 days, with a visit at 28 days as follow-up. Subjects randomized to the placebo group will receive matching placebo tablets TID for 14 days with a follow-up visit at Day 28. Subject participation will be approximately 4 weeks.
 
Subjects will be screened for eligibility for participation in the study at the Screening/Baseline Visit 1 (Day 1) after reviewing and signing the informed consent form. Subjects meeting all inclusion/exclusion criteria will then be randomized into the study (Day 1) and begin dosing this same day. If needed, screening assessments may be completed up to 3 days prior to Day 1 (first dose) as described below.
 
It is highly recommended to complete all screening and baseline assessments on the same day the subject presents at the site due to their acute pain relief needs. However, to accommodate real world logistical issues and time constraints of either the subject or site, the site has the flexibility to allow completion of screening assessments within 3 days (-3 days) prior to Day 1

baseline assessments, deployment of study-provisioned smartphone/download of trial application on subject's smartphone, randomization, and first dose (in that order).

After completing all screening and baseline assessments by/on Day 1, subjects will receive all study drug and rescue medication (acetaminophen 500 mg) and will be instructed to begin taking their study drug that same day. Depending on the time of their clinic visit, they should be instructed to begin dosing with either the midday dose (12-2 pm) or the evening dose (6-8 pm). Subjects will be instructed to continue taking study drug TID through Day 14 and complete dosing diary and daily electronic Patient-Reported Outcomes (ePRO) assessments.

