11.2.4. Clinic Visit 3: Day 14 (+ 1 Day, End of Treatment/Early Termination)

On Day 14, subjects return to the clinic to undergo the following assessments:

- Abbreviated physical examination
- Neurological examination
- Vital signs
- Document AEs
- Subject rating of pain (NRS) “right now” via the site study-provisioned tablet
- Subject rating of medication helpfulness via the site study-provisioned tablet
- Global clinical impression of improvement by the physician (CGI-C) via the site study-provisioned tablet
- Global impression of improvement by the subject (PGI-C) via the site study-provisioned tablet
- Functionality assessment:
 - Fingers to Floor Distance (FFD)
- Alcohol breathalyzer and urine drug screen
- Disability assessment:
 - Oswestry Disability Index (ODI) via the site study-provisioned tablet
- Urine pregnancy test for all females of childbearing potential
- Laboratory evaluations

- 12-Lead ECG
- Any changes or additions to prior concurrent medication use will be recorded. Confirm that no rescue medications were taken on Day 14 (Visit 3).
- Site staff to review returned study drug and rescue medication against the eDiary dosing information to evaluate compliance.
- Site staff to collect smartphone, if provisioned

In the event that a subject discontinues or is withdrawn from the study early, the Day 14/EOT assessments should be completed at an Early Termination visit.

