13. STUDY DRUG

The Sponsor will supply tolperisone 50, 100, 150, and 200 mg tablets and matching placebo in a blinded fashion. Each subject will be provided with one bottle of study drug containing 42 tablets for 14 days of TID dosing. The study drug will be self-administered (TID) by the subjects. Each subject will also be provided with one bottle of rescue medication (acetaminophen 500 mg) containing 50 caplets (as is standard commercial packaging).

Study drug and rescue medication should be stored at controlled room temperature (15-30 °C [59-86 °F]) and locked in a secure cabinet or room.

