13.1. Study Drug Administration

Tolperisone 50, 100, 150, and 200 mg, or matching placebo should be taken by the subjects TID, at 6-8 am, 12-2 pm, and 6-8 pm on Days 2 to 14; the first dose of study drug will be administered by the subject on Day 1.

All study medications will be administered orally with approximately 4-6 ounces of water. The subjects will be instructed to swallow the study tablet whole, without chewing the tablet. The subjects may take the study drug with or without food.

Subjects will be prompted via reminders on their smartphone/trial application to take their study drug at least 1 hour before and within 2 hours of the morning and evening assessments.

- Subjects in Group A (n=80) will be randomized to receive (1) 50 mg tolperisone tablet, TID for 14 days, for a total daily dose of 150 mg.
- Subjects in Group B (n=80) will be randomized to receive (1) 100 mg tolperisone tablet administered TID for 14 days, for a total daily dose of 300 mg.
- Subjects in Group C (n=80) will be randomized to receive (1) 150 mg tolperisone tablet administered TID for 14 days, for a total daily dose of 450 mg.
- Subjects in Group D (n=80) will be randomized to receive (1) 200 mg tolperisone tablet administered TID for 14 days, for a total daily dose of 600 mg.
- Subjects in Group E (n=80) will be randomized to receive (1) placebo tablet administered TID for 14 days.

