All **lighter shaded** rows are to be completed **at the clinic site and on the study-provisioned tablet** by the Investigator Rater/Evaluator or subject, as applicable for assessments.

All non-shaded rows are not captured in a study-provisioned site tablet or a subject smartphone/trial application; applicable information should be entered into the eCRF.

EOT = End of Treatment; ePRO = electronic Patient Reported Outcomes; PK = pharmacokinetic

- ^a Screening assessments may be completed within 3 days prior to Day 1 (-3 to 0 days). If screening assessments are completed prior to Day 1, inclusion/exclusion criteria to be re-reviewed for qualification of the subject's enrollment into the study prior to dosing on Day 1.
- ^b Including sex, age, race, ethnicity, body weight (kg), height (cm), body mass index (BMI) (kg/m²), and smoking habits.
- ^c Physical and neurological examination will be performed at Screening/Baseline (Day 1), on Day 4, and on Day 14. A physical examination only will be performed on Day 28. A complete physical examination will be performed at Screening/Baseline (Day 1). All other physical examinations may be disease-specific and symptom directed.
- ^d Laboratory Evaluations include hematology, serum chemistry, and urinalysis on Days 1 and 14. (See ACM lab manual for further instructions.)
- ^e DNA genotyping for CYP450 2D6 polymorphism will be collected at same time of other required blood draw on Day 1. (See Machaon lab manual for further instructions.)
- ^f For the select group of sites and subjects who will undergo PK assessments, blood samples will be drawn on Day 4. (See ACM lab manual for further instructions.)

- g Dosing will be three times per day, with a single tablet administered at each dose. Subjects should be instructed to dose at 6-8 am, 12-2 pm, and 6-8 pm for 14 days and will enter their dosing information in the eDiary on the subject's smartphone/trial application.
- h Subject rating of pain using Numerical Rating Scale (NRS, a scale of 0 to 10 where 0 = no pain, and 10=worst possible pain) for the level of pain that the subject is feeling "right now" due to back spasm (**primary efficacy endpoint**) administered by study-provisioned tablet ePRO at baseline, and on Days 4 and 14 in the clinic.
- i Subject rating of medication helpfulness (SRMH): a five point scale from 1=poor to 5=excellent, administered by study-provisioned tablet ePRO on Days 4 and 14 in the clinic.

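### The primary pain rating may be taken on Day 15, but the written dosing instructions stop at Day 14: a minor gap with a cheap wording fix

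*Protocol*

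**What the plan says.** **Visit.** Protocol 10.1, 11.2.4 and Table 2 set Visit 3 at Day 14 with a window of plus one day. The primary rating (Protocol 8.3 and 17.4.2.1) is made on the site tablet at that visit.

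**Dosing.** Protocol 10.1 reads: "Subjects will be instructed to continue taking study drug TID through Day 14 and complete dosing diary and daily ePRO assessments". The Synopsis and SAP 6.1 say the same. Protocol 13.1 gives the clock times as "at 6-8 am, 12-2 pm, and 6-8 pm on Days 2 to 14". Other places give a length only, for example Table 2 footnote g: "Subjects should be instructed to dose at 6-8 am, 12-2 pm, and 6-8 pm for 14 days". Supply is "one bottle of study drug containing 42 tablets for 14 days of TID dosing" (Protocol 13), and on Day 1 subjects start with the midday or the evening dose (Protocol 10.1).

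**Timing of dose and rating.** The one rule linking the two is the app reminder in Protocol 13.1, "to take their study drug at least 1 hour before and within 2 hours of the morning and evening assessments". It concerns the home diary, not the clinic rating.

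**Signs that dosing may run to the visit.** Table 2 marks study drug dosing in the Visit 3 column. SAP 7.4.3 (Table 4) counts one to three expected doses on the end-of-treatment day. SAP 7.5.1 plans 42 doses per subject.

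**Analysis.** SAP 7.1.2 uses the nominal visit for clinic data. SAP 7.4.4 counts as Day 14 anyone who completed the scheduled Visit 3. The per-protocol definition in SAP 7.2 does not remove an in-window Day 15 rating.

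**The concern.** The objective is the efficacy of the daily doses (Protocol 8.1), and a 'right now' item reads pain at the moment of asking. A subject seen on Day 14 has normally had at least that morning's dose. A subject seen on Day 15 who follows the wording took the last dose the evening before. The two ratings enter the primary model as the same thing, and no planned analysis of the clinic item separates them. The same-time-of-day rule for finger-to-floor distance (Protocol 12.6) may steady the hour of the visit, but not whether drug was taken that day.

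At stake is a slightly blurred primary measurement: if relief fades overnight, every dose looks a little closer to placebo and the trend test loses some power.

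**Working it through.** **1. Tablets left after the Day 14 evening dose.** Days 2 to 14 hold 13 × 3 = 39 doses.
- Midday start: 2 + 39 = 41 used, 42 − 41 = 1 left.
- Evening start: 1 + 39 = 40 used, 42 − 40 = 2 left.

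SAP Table 4 agrees: 3 × 14 − 1 = 41 (row 6) and 3 × 14 − 2 = 40 (row 9). If the leftovers are taken on Day 15, a midday start ending with a morning dose gives 3 × 15 − 3 = 42 (row 4), and an evening start ending with a midday dose gives 3 × 15 − 3 = 42 (row 8). A morning start (row 3) would use all 42 by Day 14, but Protocol 10.1 does not offer it.

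**2. Hours from last dose to rating.** Clinic hours of 8 am to 5 pm are my assumption; the documents give none.
- Day 15, wording followed: from 8 pm to 8 am is 12 h; from 6 pm to 5 pm is 23 h.
- Day 14: at most about 8 h (6 am dose, rating just before a 2 pm midday dose).

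**3. Reproducing the plan's power.** Inputs from Protocol 17.2: 80 per arm, difference 0.9, SD 2.0 (effect 0.45), two-sided 5%. The two-sample noncentral t on 158 df gives 80.8%, against 81% in Table 1. For the trend I used contrast (−2, −1, 0, 1, 2) on 395 df, with noncentrality = Σcᵢmᵢ / √(Σcᵢ² / 80), where mᵢ are the Table 1 differences in SD units. All 20 rows reproduce within 1 point. Two examples:
- 0.11/0.22/0.33/0.45: (−0.11 + 0.33 + 0.90) / √(10/80) = 1.12 / 0.3536 = 3.17, power 88.5% (Table 1: 88%).
- 0.1/0.2/0.3/0.4: (−0.1 + 0.3 + 0.8) / 0.3536 = 2.83, power 80.6% (Table 1: 81%).

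**4. Dilution.** Let f be the share of ratings made on Day 15 without a dose that day, equal across arms, and k the share of effect lost by then. Both are assumptions. The effect is multiplied by 1 − f·k, and 80 per arm acts like 80 × (1 − f·k)².

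| f·k | Example | 0.9 points becomes | Trend power, 0.11–0.45 row | Trend power, 0.1–0.4 row | Acts like n per arm |
|---|---|---|---|---|---|
| 0 | f = 0 or k = 0 | 0.90 | 88.5% | 80.6% | 80 |
| 0.02 | f = 4%, k = 0.5 | 0.88 | 87.2% | 79.0% | 77 |
| 0.05 | f = 10%, k = 0.5 | 0.86 | 85.1% | 76.4% | 72 |
| 0.10 | f = 20%, k = 0.5 | 0.81 | 81.2% | 71.9% | 65 |
| 0.25 | f = 25%, k = 1 (extreme) | 0.68 | 65.9% | 56.2% | 45 |

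**The case against.** The strongest reply is that the documents already lean toward dosing up to the visit. Table 2 marks dosing at Visit 3, Table 4 expects doses on the end-of-treatment day, and with the starts on offer the 42nd planned dose falls on Day 15. This stands in part: some subjects would dose on Day 15 anyway. A reader might infer that all Day 15 ratings are off drug, or that the documents contradict each other. Neither follows. The marks are compatible with Day 15 dosing; they just do not tell the subject to do it.

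Other points also stand:
- The regimen has a normal overnight gap of 10 to 14 h (6–8 pm to 6–8 am), so the low end of the 12 to 23 h range is routine.
- SAP 7.4.5.2 tests the past-hour and past-12-hour diary NRS at Day 14, and SAP 7.1.2 places diary data by study day and limits their analysis to Days 1 to 14. These related readouts cannot be touched by a late visit, though they do not replace the clinic item.
- Protocol 7.1 reports no accumulation and no next-day residual effects at 150 mg TID. That was a sedation study in healthy volunteers, so it does not settle how long pain relief lasts.
- A reader might infer that rescue acetaminophen is allowed on a Day 15 visit, because Protocol 11.2.4 and 14 name Day 14. Protocol 7.3.2 and 12.8 already tie the ban to clinic visit days, so this is only loose wording.

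**Conclusion.** The gap is real and minor. Visit 3 may fall on Day 15, the worded instructions that name a last dosing day name Day 14, and the rating is analysed as Day 14. A subject who follows the wording and attends a day late is rated without that day's dose or doses.

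The only expected effect is dilution toward placebo. The rule is the same in every blinded arm, and with no true effect there is nothing to dilute. A reader might therefore infer bias in favour of the drug or an inflated type I error; the documents support neither.

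Nor do they support calling the trial underpowered on this ground. The power losses shown rest on two assumed inputs, on no other loss of information, and on equal shares across arms. The loss may be zero, if no visits fall on Day 15, if those subjects dose anyway, or if relief lasts the day. The case for acting is that the change is cheap.

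**What to change.** **Dosing wording.** In the Protocol Synopsis (Study Design), Protocol 10.1 and 13.1, Table 2 footnote g and SAP 6.1, state that dosing continues on schedule until the Visit 3 rating is done, including on Day 15 if the visit falls then, using the tablets left from the 42 supplied. Bring the wording that gives only 14 days into line in the Synopsis (Test Product) and Protocol 7.3.2.

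**App.** Make sure it prompts and records Day 15 doses; Protocol 19.2 describes home capture over 14 days of treatment.

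**Scheduling.** An evening start leaves tablets for the Day 15 morning and midday doses. A midday start leaves only the morning dose, so preferably hold a Day 15 visit for those subjects before 2 pm. That keeps time since dose at or below about 8 h, as on Day 14.

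**Optional.** Align the rescue wording in Protocol 11.2.4 and 14 with the visit-day ban in 7.3.2 and 12.8.

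**Cost.** A sentence in each place, a small app change, up to two further doses for late attenders within the planned 42, and slightly less scheduling freedom. No extra drug supply or analysis is needed.

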10.2. Subject Assignment

Randomization will occur only after the subject has been determined to be eligible for study participation based on the inclusion and exclusion criteria. Subjects will be randomly assigned to one of the following five treatment groups in a 1:1:1:1:1 ratio: tolperisone 50 mg TID (150 mg/day), tolperisone 100 mg TID (300 mg/day), tolperisone 150 mg TID (450 mg/day), tolperisone 200 mg TID (600 mg/day), matching placebo TID. Prior to each eligible subject's participation, the next unique, sequentially available randomization number will be assigned to the subject using an interactive web response system.

10.2.1. Unblinding

The blind must not be broken during the course of the study unless in the opinion of the Investigator, it is absolutely necessary to safely treat a medical emergency of the subject. The decision to break the blind in emergency situations remains the responsibility of the Investigator, which will not be delayed or refused by the Sponsor. However, the Investigator should contact the Medical Monitor and Sponsor prior to breaking the blind to discuss unblinding, mainly in the interest of the subject. If it is medically imperative to know what study drug the subject is receiving, study drug should be temporarily discontinued if, in the opinion of the Investigator, continuing study drug can negatively affect the outcome of the subject's treatment.

The Principal Investigator has the ability to unblind single subjects within EDC system for emergency unblinding purposes. The Investigator should promptly notify the Medical Monitor of the emergency unblinding and the reason for breaking the blind, which should be clearly documented by the Investigator in the patient's source documentation.

10.3. Treatment Compliance

Each subject will be instructed on the importance of returning his or her study drug and rescue medication at each applicable study visit (i.e., Visits 2 and 3). The subject will also be asked to enter daily dosing information on the smartphone/trial application and study staff will review this information with the subject at each site visit to assess the subject's compliance with the study drug and rescue medication. Any missed doses will be noted by the subject on the smartphone/trial application.

11. DAILY STUDY ACTIVITIES

A complete Schedule of Procedures can be found in [Table 2](#).

11.1. Screening

The Screening/Baseline visit (Visit 1) will include procedures as listed in [Table 2](#).

The informed consent document will be discussed with each potential participant, and each individual will sign an informed consent document for the study prior to any study-specific procedures being performed. A positive test result for pregnancy, urine drug or alcohol breathalyzer will end the screening process.

11.2. Study Periods

See [Table 2](#) in [Section 29](#) for the schedule of procedures and assessments across the time points for the study.

11.2.1. Clinic Visit 1: Day 1 (Screening/Baseline) and up to Day -3 (Additional Screening Days, If Needed)

Subjects will visit the clinic site for their Screening/Baseline visit (Visit 1, -3 to 0 days) and undergo screening processes for entry into the study. Subjects who meet the inclusion and no exclusion criteria will be entered into the study.

The following screening assessments will be conducted by the Investigator or designee prior to subject enrollment. If needed, the following screening assessments may be completed within 3 days prior to Day 1 (-3 to 0 days):

- Informed consent to be signed
- A urine pregnancy test for all females of childbearing potential
- Medical history and demographic data, including sex, age, race, ethnicity, body weight (kg), height (cm), body mass index (BMI) (kg/m^2), and smoking habits
- Physical examination
- Neurological examination
- The alcohol breathalyzer and urine drug screen
- Laboratory tests (serum chemistry, hematology, and urinalysis)
 - blood sample for DNA genotyping for CYP450 2D6 polymorphism would be collected at same time of other required blood draw
- Vital signs (supine and standing blood pressure [including orthostatic pressure], sitting heart rate (after approximately 3 minutes at rest), respiratory rate, and body temperature,)
- A 12-lead ECG
- Prior and/or concomitant medications during the study will be recorded, as well as those that qualify as rescue medications (see [Section 12.8](#))
- Inclusion/exclusion criteria to be reviewed for qualification of the subject's enrollment into the study

The following baseline assessments will be conducted by the Investigator or designee prior to dosing on Day 1. If any screening assessments were completed prior to Day 1, inclusion/exclusion criteria are to be re-reviewed for qualification of the subject's enrollment into the study:

- Baseline assessments for study efficacy endpoints:
 - Subject rating of pain “right now” (NRS), must be 4 or greater

- Global severity of pain assessment by the physician and the subject on a scale of 1-5, with 1=none, 2=mild, 3=moderate, 4=severe, 5=very severe
- Functionality assessment:
 - Fingers to Floor Distance (FFD)
- Disability assessment:
 - Oswestry Pain and Disability Index (ODI) via the site study-provisioned tablet
- Deploy subject smartphone/use of trial application to subject
- Quality of sleep via the subject smartphone/use of trial application
- Randomization
- Dispense study drug (for 14 days of dosing) and rescue medication; sufficient for use by subjects for the entire duration of the study
- AEs occurring after the first dose of study medication will be reported. Any concurrent medication use will be recorded.

Subjects will receive all study drug and rescue medication on Day 1. Subjects will begin taking their study drug that same day. Depending on the time of their clinic visit, they should be instructed to begin dosing with either the midday dose (12-2 pm) or the evening dose (6-8 pm).

Subjects will be provided a smartphone/use of trial application on Day 1, just prior to randomization. Subjects will be instructed on how to perform the assessments to be conducted by the subject at home/away from clinic and how to record the results on the smartphone/trial application.

Subjects will be instructed to return to the clinic on Day 4 (Visit 2) and on Day 14 (EOT visit, Visit 3) and to bring all study drug and rescue medication with them as well as smartphone device. Subjects must also return to the clinic for a safety follow-up visit on Day 28 (2-week follow-up visit, Visit 4).

Subjects will be asked and reminded not to consume alcoholic beverages prior to their study visit on Days 1, 4, and 14 and to restrict their consumption during the study duration. At all other times, alcohol consumption is limited to no more than 2 alcoholic drinks or equivalent (beer [24 ounces or 710 mLs], wine [12 ounces or 355 mLs], or distilled spirits [3 ounces or 89 mLs]) per day.

Subjects will be reminded to restrict their consumption of caffeinated beverages to no more than 4 units per day amounts (1 unit =120 mg caffeine or about one eight-ounce cup of coffee).

Subjects will be reminded to refrain from vigorous physical activity, heat and ice packs, and non-pharmacological therapies (e.g., acupuncture, chiropractic adjustment, massage therapy, TENS, physiotherapy) during Days 1 to 14.

